10 APPENDICES

10.1 Appendix 1: SF-36 v2

Your Health and Well-Being

This survey asks for your views about your health. This information will help keep track of how you feel and how well you are able to do your usual activities. *Thank you for completing this survey!*

For each of the following questions, please tick the one box that best describes your answer.

1. In general, would you say your health is:

Excellent	Very good	Good	Fair	Poor
▼	▼	▼	▼	▼
 1	 2	 3	 4	 5

2. Compared to one year ago, how would you rate your health in general now?

Much better now than one year ago	Somewhat better now than one year ago	About the same as one year ago	Somewhat worse now than one year ago	Much worse now than one year ago
▼	▼	▼	▼	▼
 1	 2	 3	 4	 5

SF-36 v2

3. The following questions are about activities you might do during a typical day. Does your health now limit you in these activities? If so, how much?

Yes, limited a lot	Yes, limited a little	No, not limited at all
▼	▼	▼

- a Vigorous activities, such as running, lifting heavy objects, participating in strenuous sports 1 2 3
- b Moderate activities, such as moving a table, pushing a vacuum cleaner, bowling, or playing golf 1 2 3
- c Lifting or carrying groceries 1 2 3
- d Climbing several flights of stairs 1 2 3
- e Climbing one flight of stairs 1 2 3
- f Bending, kneeling, or stooping 1 2 3
- g Walking more than a mile 1 2 3
- h Walking several hundred yards 1 2 3
- i Walking one hundred yards 1 2 3
- j Bathing or dressing yourself 1 2 3

SF-36 v2

4. During the past 4 weeks, how much of the time have you had any of the following problems with your work or other regular daily activities as a result of your physical health?

	All of the time	Most of the time	Some of the time	A little of the time	None of the time
	▼	▼	▼	▼	▼
a Cut down on the amount of time you spent on work or other activities	 1	 2	 3	 4	 5
b Accomplished less than you would like	 1	 2	 3	 4	 5
c Were limited in the kind of work or other activities	 1	 2	 3	 4	 5
d Had difficulty performing the work or other activities (for example, it took extra effort)	 1	 2	 3	 4	 5

5. During the past 4 weeks, how much of the time have you had any of the following problems with your work or other regular daily activities as a result of any emotional problems (such as feeling depressed or anxious)?

	All of the time	Most of the time	Some of the time	A little of the time	None of the time
	▼	▼	▼	▼	▼
a Cut down on the amount of time you spent on work or other activities	 1	 2	 3	 4	 5
b Accomplished less than you would like	 1	 2	 3	 4	 5
c Did work or other activities less carefully than usual	 1	 2	 3	 4	 5

SF-36 v2

6. During the past 4 weeks, to what extent has your physical health or emotional problems interfered with your normal social activities with family, friends, neighbours, or groups?

Not at all	Slightly	Moderately	Quite a bit	Extremely
▼	▼	▼	▼	▼
 _1	 _2	 _3	 _4	 _5

7. How much bodily pain have you had during the past 4 weeks?

None	Very mild	Mild	Moderate	Severe	Very severe
▼	▼	▼	▼	▼	▼
 _1	 _2	 _3	 _4	 _5	 _6

8. During the past 4 weeks, how much did pain interfere with your normal work (including both work outside the home and housework)?

Not at all	A little bit	Moderately	Quite a bit	Extremely
▼	▼	▼	▼	▼
 _1	 _2	 _3	 _4	 _5

SF-36 v2

9. These questions are about how you feel and how things have been with you during the past 4 weeks. For each question, please give the one answer that comes closest to the way you have been feeling. How much of the time during the past 4 weeks...

	All of the time	Most of the time	Some of the time	A little of the time	None of the time	
	▼	▼	▼	▼	▼	
a	Did you feel full of life?	 1  2  3  4  5
b	Have you been very nervous? ...	 1  2  3  4  5
c	Have you felt so down in the dumps that nothing could cheer you up?	 1  2  3  4  5
d	Have you felt calm and peaceful?	 1  2  3  4  5
e	Did you have a lot of energy?	 1  2  3  4  5
f	Have you felt downhearted and low?	 1  2  3  4  5
g	Did you feel worn out?	 1  2  3  4  5
h	Have you been happy?	 1  2  3  4  5
i	Did you feel tired?	 1  2  3  4  5

10. During the past 4 weeks, how much of the time has your physical health or emotional problems interfered with your social activities (like visiting with friends, relatives, etc.)?

All of the time	Most of the time	Some of the time	A little of the time	None of the time
▼	▼	▼	▼	▼
 1	 2	 3	 4	 5

[figure not shown]
SF-36 v2

11. How TRUE or FALSE is each of the following statements for you?

	Definitely true	Mostly true	Don't know	Mostly false	Definitely false
a I seem to get ill more easily than other people	 1	 2	 3	 4	 5
b I am as healthy as anybody I know	 1	 2	 3	 4	 5
c I expect my health to get worse	 1	 2	 3	 4	 5
d My health is excellent	 1	 2	 3	 4	 5

Thank you for completing these questions!

SF-36 Model

10.2 Appendix 2: FACT-An (Version 4)

10.2.1 FACT-An Questionnaire

Below is a list of statements that other people with your illness have said are important. Please circle or mark one number per line to indicate your response as it applies to the past 7 days.

PHYSICAL WELL-BEING		Not at all	A little bit	Some-what	Quite a bit	Very much
GP1	I have a lack of energy	0	1	2	3	4
GP2	I have nausea	0	1	2	3	4
GP3	Because of my physical condition, I have trouble meeting the needs of my family	0	1	2	3	4
GP4	I have pain	0	1	2	3	4
GP5	I am bothered by side effects of treatment	0	1	2	3	4
GP6	I feel ill	0	1	2	3	4
GP7	I am forced to spend time in bed	0	1	2	3	4
SOCIAL/FAMILY WELL-BEING						
GS1	I feel close to my friends	0	1	2	3	4
GS2	I get emotional support from my family	0	1	2	3	4
GS3	I get support from my friends	0	1	2	3	4
GS4	My family has accepted my illness	0	1	2	3	4
GS5	I am satisfied with family communication about my illness	0	1	2	3	4
GS6	I feel close to my partner (or the person who is my main support)	0	1	2	3	4
Q1	Regardless of your current level of sexual activity, please answer the following question. If you prefer not to answer it, please mark this box  and go to the next section.					
GS7	I am satisfied with my sex life	0	1	2	3	4

FACT-An (Version 4)

Please circle or mark one number per line to indicate your response as it applies to the past 7 days.

EMOTIONAL WELL-BEING		Not at all	A little bit	Some-what	Quite a bit	Very much
GE1	I feel sad	0	1	2	3	4
GE2	I am satisfied with how I am coping with my illness	0	1	2	3	4
GE3	I am losing hope in the fight against my illness	0	1	2	3	4
GE4	I feel nervous	0	1	2	3	4
GE5	I worry about dying	0	1	2	3	4
GE6	I worry that my condition will get worse	0	1	2	3	4

FUNCTIONAL WELL-BEING		Not at all	A little bit	Some-what	Quite a bit	Very much
GF1	I am able to work (include work at home)	0	1	2	3	4
GF2	My work (include work at home) is fulfilling	0	1	2	3	4
GF3	I am able to enjoy life	0	1	2	3	4
GF4	I have accepted my illness	0	1	2	3	4
GF5	I am sleeping well	0	1	2	3	4
GF6	I am enjoying the things I usually do for fun	0	1	2	3	4
GF7	I am content with the quality of my life right now	0	1	2	3	4

FACT-An (Version 4)

Please circle or mark one number per line to indicate your response as it applies to the past 7 days.

ADDITIONAL CONCERNS		Not at all	A little bit	Some- what	Quite a bit	Very much
HI7	I feel fatigued	0	1	2	3	4
HI12	I feel weak all over	0	1	2	3	4
An1	I feel listless ("washed out")	0	1	2	3	4
An2	I feel tired	0	1	2	3	4
An3	I have trouble starting things because I am tired	0	1	2	3	4
An4	I have trouble finishing things because I am tired ..	0	1	2	3	4
An5	I have energy	0	1	2	3	4
An6	I have trouble walking	0	1	2	3	4
An7	I am able to do my usual activities	0	1	2	3	4
An8	I need to sleep during the day	0	1	2	3	4
An9	I feel lightheaded (dizzy)	0	1	2	3	4
An10	I get headaches	0	1	2	3	4
B1	I have been short of breath	0	1	2	3	4
An11	I have pain in my chest	0	1	2	3	4
An12	I am too tired to eat	0	1	2	3	4
BL4	I am interested in sex	0	1	2	3	4
An13	I am motivated to do my usual activities	0	1	2	3	4
An14	I need help doing my usual activities	0	1	2	3	4
An15	I am frustrated by being too tired to do the things I want to do	0	1	2	3	4
An16	I have to limit my social activity because I am tired	0	1	2	3	4

10.2.2 FACT-An Scoring Guidelines

- Instructions:*
1. Record answers in "item response" column. If missing, mark with an X
 2. Perform reversals as indicated, and sum individual items to obtain a score.
 3. Multiply the sum of the item scores by the number of items in the subscale, then divide by the number of items answered. This produces the subscale score.
 4. Add subscale scores to derive total scores (TOI, FACT-G & FACT-An).
 5. **The higher the score, the better the QOL.**

Subscale	Item Code	Reverse item?	Item response	Item Score
PHYSICAL WELL-BEING (PWB)	GP1	4 -	_____	= _____
	GP2	4 -	_____	= _____
	GP3	4 -	_____	= _____
	GP4	4 -	_____	= _____
	GP5	4 -	_____	= _____
	GP6	4 -	_____	= _____
	GP7	4 -	_____	= _____
Score range: 0-28				
			Sum individual item scores: _____	
			Multiply by 7: _____	
			Divide by number of items answered: _____	
				=PWB subscale score
SOCIAL/FAMILY WELL-BEING (SWB)	GS1	0 +	_____	= _____
	GS2	0 +	_____	= _____
	GS3	0 +	_____	= _____
	GS4	0 +	_____	= _____
	GS5	0 +	_____	= _____
	GS6	0 +	_____	= _____
	GS7	0 +	_____	= _____
Score range: 0-28				
			Sum individual item scores: _____	
			Multiply by 7: _____	
			Divide by number of items answered: _____	
				=SWB subscale score
EMOTIONAL WELL-BEING (EWB)	GE1	4 -	_____	= _____
	GE2	0 +	_____	= _____
	GE3	4 -	_____	= _____
	GE4	4 -	_____	= _____
	GE5	4 -	_____	= _____
	GE6	4 -	_____	= _____
Score range: 0-24				
			Sum individual item scores: _____	
			Multiply by 6: _____	
			Divide by number of items answered: _____	
				=EWB subscale score

FUNCTIONAL WELL-BEING (FWB)	GF1	0	+	_____	= _____
	GF2	0	+	_____	= _____
	GF3	0	+	_____	= _____
	GF4	0	+	_____	= _____
	GF5	0	+	_____	= _____
	GF6	0	+	_____	= _____
	GF7	0	+	_____	= _____

Score range: 0-28

Sum individual item scores: _____
 Multiply by 7: _____
 Divide by number of items answered: _____
 = FWB subscale score

Subscale	Item Code	Reverse item?	Item response	Item Score	
ANEMIA SUBSCALE (AnS)	HI7	4	-	_____	= _____
	HI12	4	-	_____	= _____
	An1	4	-	_____	= _____
	An2	4	-	_____	= _____
	An3	4	-	_____	= _____
	An4	4	-	_____	= _____
	An5	0	+	_____	= _____
	An6	4	-	_____	= _____
	An7	0	+	_____	= _____
	An8	4	-	_____	= _____
	An9	4	-	_____	= _____
	An10	4	-	_____	= _____
	B1	4	-	_____	= _____
	An11	4	-	_____	= _____
	An12	4	-	_____	= _____
	BL4	0	+	_____	= _____
An13	0	+	_____	= _____	
An14	4	-	_____	= _____	
An15	4	-	_____	= _____	
An16	4	-	_____	= _____	

Score range: 0-80

Sum individual item scores: _____
 Multiply by 20: _____
 Divide by number of items answered: _____
 = An Subscale score

To derive a FACT-An Trial Outcome Index (TOI):

Score range: 0-136

$$\frac{\text{_____}}{\text{(PWB score)}} + \frac{\text{_____}}{\text{(FWB score)}} + \frac{\text{_____}}{\text{(AnS score)}} = \text{_____} = \text{FACT-An TOI}$$

To Derive a FACT-G total score:

Score range: 0-108

$$\frac{\text{_____}}{\text{(PWB score)}} + \frac{\text{_____}}{\text{(SWB score)}} + \frac{\text{_____}}{\text{(EWB score)}} + \frac{\text{_____}}{\text{(FWB score)}} = \text{_____} = \text{FACT-G Total score}$$

To Derive a FACT-An total score:

Score range: 0-188

$$\frac{\text{PWB score}}{\text{PWB score}} + \frac{\text{SWB score}}{\text{SWB score}} + \frac{\text{EWB score}}{\text{EWB score}} + \frac{\text{FWB score}}{\text{FWB score}} + \frac{\text{AnS score}}{\text{AnS score}} = \text{FACT-An Total score}$$

*For guidelines on handling missing data and scoring options, please refer to the Administration and Scoring Guidelines in the manual or on-line at www.facit.org.

FACIT-Fatigue Subscale Scoring Guidelines

- Instructions:*
1. Record answers in "item response" column. If missing, mark with an X
 2. Perform reversals as indicated, and sum individual items to obtain a score.
 3. Multiply the sum of the item scores by the number of items in the subscale, then divide by the number of items answered. This produces the subscale score.
 4. **The higher the score, the better the QOL.**

Subscale Score	Item Code	Reverse item?	Item response	Item
FATIGUE SUBSCALE	HI7	4 -	_____	= _____
	HI12	4 -	_____	= _____
	An1	4 -	_____	= _____
	An2	4 -	_____	= _____
	An3	4 -	_____	= _____
	An4	4 -	_____	= _____
	An5	0 +	_____	= _____
	An7	0 +	_____	= _____
	An8	4 -	_____	= _____
	An12	4 -	_____	= _____
	An14	4 -	_____	= _____
	An15	4 -	_____	= _____
	An16	4 -	_____	= _____

Score range: 0-52

Sum individual item scores: _____
Multiply by 13: _____
Divide by number of items answered: _____
 = **Fatigue Subscale score**

10.3 Appendix 3: EQ-5D 5L v2

Under each heading, please tick the ONE box that best describes your health TODAY

MOBILITY

- I have no problems in walking about
- I have slight problems in walking about
- I have moderate problems in walking about
- I have severe problems in walking about
- I am unable to walk about

SELF-CARE

- I have no problems washing or dressing myself
- I have slight problems washing or dressing myself
- I have moderate problems washing or dressing myself
- I have severe problems washing or dressing myself
- I am unable to wash or dress myself

USUAL ACTIVITIES (e.g. work, study, housework, family or leisure activities)

- I have no problems doing my usual activities
- I have slight problems doing my usual activities
- I have moderate problems doing my usual activities
- I have severe problems doing my usual activities
- I am unable to do my usual activities

PAIN / DISCOMFORT

- I have no pain or discomfort
- I have slight pain or discomfort
- I have moderate pain or discomfort
- I have severe pain or discomfort
- I have extreme pain or discomfort

ANXIETY / DEPRESSION

[figure not shown]
- I am not anxious or depressed
- I am slightly anxious or depressed
- I am moderately anxious or depressed
- I am severely anxious or depressed
- I am extremely anxious or depressed

EQ-5D 5L v2

- We would like to know how good or bad your health is TODAY.
- This scale is numbered from 0 to 100.
- 100 means the best health you can imagine.
0 means the worst health you can imagine.
- Mark an X on the scale to indicate how your health is TODAY.
- Now, please write the number you marked on the scale in the box below.

YOUR HEALTH TODAY =

The best health
you can imagine

The worst health
you can imagine

10.4 Appendix 4: WPAI:ANS V2.0

The following questions ask about the effect of your anaemic symptoms on your ability to work and perform normal daily activities. *Please fill in the blanks or circle a number, as indicated.*

1. Are you currently employed (working for pay)? _____ NO _____ YES
If NO, tick "NO" and skip to question 6.

The next questions refer to the **past seven days**, not including today.

2. During the past seven days, how many hours did you miss from work because of problems associated with your anaemic symptoms? *Include hours you missed on sick days, times you went in late, left early, etc., because of your anaemic symptoms . Do not include time you missed to participate in this study.*

_____ HOURS

3. During the past seven days, how many hours did you miss from work because of any other reason, such as annual leave, holidays, time off to participate in this study?

_____ HOURS

4. During the past seven days, how many hours did you actually work?

_____ HOURS (If "0", skip to question 6)

[figure not shown]
5. During the past seven days, how much did your anaemic symptoms affect your productivity while you were working?

Think about days you were limited in the amount or kind of work you could do, days you accomplished less than you would like, or days you could not do your work as carefully as usual.

If anaemic symptoms affected your work only a little, choose a low number. Choose a high number if anaemic symptoms affected your work a great deal.

WPAI:ANS

Consider only how much anaemic symptoms affected productivity while you were working.

[figure not shown]

CIRCLE A NUMBER

6. During the past seven days, how much did your anaemic symptoms affect your ability to perform your normal daily activities, other than work at a job?

By normal activities, we mean the usual activities you perform, such as working around the house, shopping, childcare, exercising, studying, etc. Think about times you were limited in the amount or kind of activities you could perform and times you accomplished less than you would like. If anaemic symptoms affected your activities only a little, choose a low number. Choose a high number if anaemic symptoms affected your activities a great deal.

Consider only how much anaemic symptoms affected your ability to do your normal daily activities, other than work at a job.

CIRCLE A NUMBER

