6.1.3.14.4 Work Productivity and Activity Impairment (WPAI: ANS)

The objective of the Work Productivity and Activity Impairment questionnaire: Anemic Symptoms v2 (WPAI: ANS) is to measure work and activity impairment during the past seven days due to anemia. It is self-assessed. The WPAI: ANS consists of 6 questions, including asking if the subject is working, how many hours the person missed work due to anemic symptoms, how many hours the subject actually worked and how the anemic symptoms impacted the productivity and ability to do daily activities (see Appendix [10.4](#)).

For subjects who are currently employed, the following four items will be calculated:

- Percent work time missed due to anaemic symptoms: $100 \times Q2 / (Q2 + Q4)$
- Percent impairment while working due to anaemic symptoms: $100 \times Q5 / 10$
- Percent overall work impairment due to anaemic symptoms: $100 \times Q2 / (Q2 + Q4) + [(1 - Q2 / (Q2 + Q4)) \times (Q5 / 10)]$
- Percent activity impairment due to anaemic symptoms: $100 \times Q6 / 10$

Change from baseline to the average value in weeks 12-28 and in weeks 36-52 will be calculated for these items, following the same rules as defined in Section [6.1.2.4](#) The evaluation period score is defined as the average of available WPAI: ANS subscore of weeks 12-28 (visit at W12 and W28) and weeks 36-52 (visit at W36 and W52).

No imputation will be performed in case of a missing item. Baseline always refers to the assessment at day 1 to be performed prior to first study drug administration.

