7 STATISTICAL METHODOLOGY

7.1 General Considerations

- All statistical comparisons will be made using two sided tests at the $\alpha=0.05$ significance level unless specifically stated otherwise. Null hypotheses for superiority testing will be of no treatment difference and corresponding alternative hypothesis will be two-sided. Null hypotheses for non-inferiority testing will be of inferiority of roxadustat treatment and will be one-sided at the $\alpha=0.025$.
- All data processing, summarization, and analyses will be performed using SAS® Version 9.3 (SAS Enterprise Guide 4.3) or higher. Specifications for tables, data listings and figures (TLFs) formats can be found in the TLF Specifications for this study.
- All data will be summarized by treatment arm (roxadustat and placebo) and for the total, unless specified otherwise.
- For continuous variables that are recorded as “< X” or “> X”, the value of “X” will be used in the calculation of summary statistics. The original values will be used for the listings.
- All percentages will be rounded to one decimal place and lined up by the decimal place. The percentage will be suppressed when the count is zero.
- Any p-values will be rounded to four decimal places and will be presented as ‘< 0.0001’ if they are less than 0.0001 after rounding.
- For continuous variables, descriptive statistics will include the number of subjects (n), mean, standard deviation, median, minimum and maximum. Frequencies and percentages will be displayed for categorical data. Percentages by categories will be based on the number of subjects with no missing data, i.e., will add up to 100%. Number of missing values will be shown in the frequencies tables
- All data included in summary tables, inferential analyses or figures will also be listed.
- Listings will be done on all randomized subjects and all assessments (all collected data in the eCRF will be listed except the physical examination data).
- Model checking will be performed using graphical outputs provided by the SAS procedures.

For the definition of subgroups of interest please refer to Section [7.8](#).

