Descriptive statistics (value, change from baseline) will be presented for SF-36 (subscale and component scores) and FACT-An (total and subscale scores) by visit and treatment arm. Mean values will also be plotted over time and by treatment arm.

In addition, for the average value in weeks 12-28, an inferential analysis, similar to the one defined in Section [7.4.2.1](#) will be performed for the following endpoints:

- Physical Component Scores of SF-36 (SF-36 PCS)
- Anemia Subscale (“Additional Concerns”) of FACT-An Scores
- Total FACT-An Scores

For SF-36, at each visit, the frequency and proportion of subjects with a change from baseline ≤ 3 points and ≤ 5 points will be reported for Physical Functioning, Vitality and Physical Component scores.

EQ-5D 5L

For the EQ-5D 5L VAS score, change from baseline to each visit and to the average of weeks 12-28 will be described by treatment arm.

For the 5 EQ-5D 5L qualitative domains, the number and percentage of subjects in each response level value will be reported by visit and treatment arm.

Work Productivity and Activity Impairment (WPAI)

The number and proportion of employed subjects will be reported by visit and treatment arm.

WPAI calculated variables will be summarized descriptively by visit and treatment arm.

Furthermore, change from baseline to each visit and to the average of weeks 12-28 and 36-52 will be described by treatment arm.

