7.11 Handling of Missing Data, Outliers, Visit Windows, and Other Information

7.11.1 Missing Data

For relevant analyses without rescue therapy, for subjects who used rescue therapy, the reported Hb values after the initiation of rescue therapy will be set to missing (instead of the reported values) for 6 weeks from the start date of rescue therapy (or the end in case the duration of rescue therapy > 1 day).

The following imputations will be performed for the continuous endpoints, unless specified otherwise :

- An MMRM model will be run for the purpose of implicit imputation of missing data by using all the available information from the observed data via the within-patient correlation structure for continuous endpoints with inferential analysis.

- An ANCOVA model with multiple imputations (MI) will also be run.

No imputations will be done for endpoints with no inferential analysis.

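### SAP 6.1.3.14.4: percent overall work impairment comes out missing for employed subjects with no hours worked and some hours lost to anaemic symptoms, although the formula's value there is exactly 100%

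*SAP*

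**What the plan says.** Question numbers below are those of the form.

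- **The form** (SAP Appendix 4; the same item is in protocol Appendix 9). Question 2 asks for hours missed because of anaemic symptoms, question 3 for hours missed for any other reason, and question 4 for hours worked. Question 5 is a 0–10 rating of lost productivity while working. Beside question 4 stands "If '0', skip to question 6", so question 5 is blank by design whenever no hours were worked.
- **The derivation** (SAP 6.1.3.14.4). The population is stated without exception: "For subjects who are currently employed, the following four items will be calculated". The third score, "Percent overall work impairment due to anaemic symptoms", is built from questions 2, 4 and 5.
- **Missing items.** The same section says "No imputation will be performed in case of a missing item". SAP 7.11.1 adds "No imputations will be done for endpoints with no inferential analysis".
- **Period score** (SAP 6.1.3.14.4). "The evaluation period score is defined as the average of available WPAI: ANS subscore of weeks 12-28", with weeks 36–52 handled the same way. Baseline is the Day 1 assessment, with no fallback.
- **Software** (SAP 7.1). "All data processing, summarization, and analyses will be performed using SAS".
- **Use** (SAP 7.4.3.14). "WPAI calculated variables will be summarized descriptively by visit and treatment arm", with change from baseline described by arm.

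**The concern.** The derivation asks for an item that the form has told some respondents not to answer. No section separates a question 5 that was skipped as instructed from one left unanswered. The records affected are not a random subset: by construction they all sit at the maximum of the score. Losing them lowers the reported mean. It also makes two of the four WPAI scores disagree for the same visit, since work time missed is 100% while overall impairment, which cannot be lower, is absent. This is separate from the scaling error on the same line, where the factor 100 multiplies only the first term, and it would remain after that error is corrected.

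**Working it through.** **Inputs.** The formula, the skip instruction and the no-imputation rule come from SAP 6.1.3.14.4 and Appendix 4. SAS arithmetic returns missing whenever an operand is missing, including zero times missing. The plan states no figure to reproduce.

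Let a = Q2/(Q2 + Q4).
- As printed: overall = 100 × a + (1 − a) × Q5/10.
- With the scaling corrected: overall = 100 × [a + (1 − a) × Q5/10].

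**Step 1. Affected record: Q2 = 40, Q4 = 0, Q5 blank.** a = 40/40 = 1. The second term is (1 − 1) × missing, which is missing, so the score is missing under either version. Percent work time missed is 100 × 1 = 100%.

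**Step 2. The value is known.** With a = 1 the weight on Q5 is 0. Q5 = 0 and Q5 = 10 both give 100%, printed or rescaled.

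**Step 3. A near neighbour is kept: Q2 = 38, Q4 = 2, Q5 = 8.** a = 0.95. Printed: 95 + 0.05 × 0.8 = 95.04%. Rescaled: 100 × (0.95 + 0.04) = 99%. The slightly less impaired record is scored and the one at the maximum is not.

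**Step 4. No hours in either category: Q2 = Q4 = 0** (for example, a week of leave). a = 0/0, so the score is missing, and rightly so.

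**Step 5. Effect on a by-visit mean.** Let f be the share of affected records and m the mean of the rest. The full mean is 100f + (1 − f)m, the reported mean is m, and the shortfall is f × (100 − m). Both f and m are assumptions.

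| f | m = 20 | m = 40 |
|---|---|---|
| 1% | 0.8 | 0.6 |
| 5% | 4.0 | 3.0 |
| 10% | 8.0 | 6.0 |

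The disagreement between scores shows in a small assumed case: nine subjects with Q2 = 0 and Q5 = 0, and one with Q2 = 40 and Q4 = 0. Mean work time missed is 10%. Reported mean overall impairment is 0%, where the formula's value is 10%.

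**Step 6. Effect on the period average.** If Week 12 is 100 but lost and Week 28 is 60, the average of available visits is 60 instead of (100 + 60)/2 = 80. The subject leaves the average altogether only if the other visit is also unavailable.

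**Step 7. Effect on change from baseline.** A baseline of 100 that is lost, followed by 60, removes a change of 60 − 100 = −40. A baseline of 60 followed by 100 at every visit, all lost, removes a change of 100 − 60 = +40. The two kinds of loss act in opposite directions.

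**The case against.** **The SAP never says these records are set to missing.** That follows from literal execution. A question skipped on instruction is arguably not a missing item, and since its weight is zero, returning 100 fills in nothing unknown. A careful programmer might well do so. This stands as far as it goes: the SAP is silent rather than prohibitive. But nothing in it directs the programmer to that reading, and the formula as written returns missing.

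**Not every such record is a week lost to anaemia.** A reader might infer that everyone dropped was fully disabled by anaemic symptoms. Question 3 shows otherwise: Q2 = 2, Q3 = 38, Q4 = 0 meets the condition with only 2 of 40 hours lost to anaemic symptoms. The formula ignores question 3 by design, so its value is still 100%, but that is a property of the score and not evidence of a lost week.

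**A reader might infer bias toward no difference between arms**, on the expectation that placebo has more such records. With an assumed 5% on placebo, 1% on roxadustat and m = 20 in both, means of 24.0 and 20.8 would both be reported as 20. That case equates the arms by construction, compares means at one visit and leaves out baseline. The documents give no frequency by arm, and Step 7 shows that the sign for change from baseline is open.

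**The consequence is small.** Protocol 5.4.6 lists WPAI as exploratory. SAP Table 5 places it among additional secondary endpoints, but it has no inferential analysis and is absent from the testing sequence in SAP Table 16. Work time missed and activity impairment are still computed for these visits, and impairment while working is properly not applicable. All of this stands and limits the importance of the point, not its correctness.

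**Conclusion.** The point holds as a derivation fault in one of four WPAI scores. Applied as written, percent overall work impairment is missing for any employed subject-visit with Q2 > 0 and Q4 = 0, where its value is exactly 100%. The by-visit mean is too low in any arm with such records, by f × (100 − m). The sizes shown rest on assumed f and m, since the documents give neither these nor the number of employed subjects. The effect on the between-arm difference in change from baseline has no determinable direction. No primary or key secondary result is touched.

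**What to change.** Add to SAP 6.1.3.14.4:

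> If Q4 = 0 and Q2 > 0, Q5 is not applicable (not a missing item) and percent overall work impairment = 100. If Q2 = Q4 = 0, percent work time missed and percent overall work impairment are missing.

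The second sentence changes no result; it records that missing is intended there. Make the edit together with the scaling correction on the same line, so that 100 multiplies the whole sum. The cost is one added rule and one line of code, with no change to the form or to data collection. SAP section 1 permits version-controlled revisions before database hard lock; after that, the change would need to be justified in the clinical study report.
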